37. Phone follow-up if permission granted by participants. Submit later.						X
38. Modified Scale for Suicidal Ideation (MSSI) – to be used as needed e.g., for triage evaluation acute suicide risks in addition to the C-SSRS	X	X	X	X	X	X
39. UCSD Brief Assessment of Capacity to Consent (UBACC)	X					X
40. Anxiety Timeline	X			X	X	X
41. Peterson Puberty Scale.PPS-Male	X			X	X	X
42a. Self-Compassion Scale (SCS) 42b. the Self Compassionate Reactions Inventory.	X			X	X	X
43. Adolescent Life Experience Survey	X			X	X	X
44. Hopelessness Scale for Children (HSC)	X	X	X	X	X	X
45a. Dimensional Anhedonia Rating Scale (DARS) 45b. Temporal Experiences of Pleasure Scale (TEPS) 45c. Positive and Negative Affect Schedule (PANAS)	X		X	X	X	X
46. Brown_Stanley Safety Plan Template	X			X	X	X
47. Suicidal Circumstances Schedule	X			X	X	X
48. Suicide Attempters Risk	X			X	X	X
49. Suicide Attempters Intent	X			X	X	X
50. Phone suitability screen script						
51. Rosenberg's Self-Esteem Scale (RSES)	X			X	X	
52. Dissociation Experience Scale (DES-2)	X	X	X	X	X	
53. Dissociation Tension Scale (DSS)	X	X	x	X	X	
54. Borderline personality questionnaire (BPQ)	X			X	X	
55. Revised Conflict Tactics Scale (CTS2)	X					
56. California Psychotherapy Alliance Scales (CALPAS)	X					
57. Working Alliance Inventory (WAI)	X					
58. Working Alliance Inventory – Short Revised (WAI-SR)	X					
59. Experiences in Close Relationships-Revised (ECR-R)	X			X	X	
60. Structured Clinical Interview for DSM-5 Personality Disorder (SCID-5-PD)	X			X	X	X

61. Structured Clinical Interview for DSM-5 Clinician Version (SCID-5-CV)	X			X	X	X
62. Minnesota Multiphasic Personality Inventory-Adolescent (MMPI-A- RF)	X			X	X	X

Study Duration: Approximately 5 - 18 months.

5.2 The duration anticipated to enroll all study participants: 5 -10 years.

5.3 The duration to complete all study procedures, long-term follow-up, data analysis: 14 - 20 years.

5.4 Use of radiation: No use of radiation.

5.5 Use of Center for Magnetic Resonance Research: Yes.

6. Data and Specimen Banking: N/A.

6.1 Not applicable.

7. Sharing of Results with Participants

7.1 Results will not be shared with participants unless guardians/parents/caregivers specifically request them in writing (via email to the PI). If so, a summary of key questionnaires, (i.e., one paragraph) will be emailed to the caregiver from [contact]. No unscored or "raw" protocols will be shared to preserve test integrity and to avoid confusing patients or

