their families about the meaning of the tests. Psychological findings and results are not recommended to be disseminated in the absence of a feedback session with a licensed mental health practitioner. However, if there are unexpected findings in the brain imaging (e.g., possible brain tumor or cyst evidence in the structural scans) the entirety of the brain imaging acquisition will be shared with the participant and their family (in a cd directly given to the parent/caregiver) and they will be instructed to consult with a radiologist and/or neurologist. The costs of that consultation are not covered by this research.

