3. **Potential loss of confidentiality.** All clinical information will be kept confidential in a secure database. Data will be stored using a study-generated identification number. Any documents with personal health information (i.e., consent forms), will be kept in a separate, locked file. Links between participant names and participant numbers will be stored in a secure database with limited access only to select study staff. Information provided by the Participants to study staff will be kept confidential from their parents, except in the case where danger to self or others is identified. In those cases, the parents will be informed, and the participant will be referred to clinically appropriate emergency care.

4. **Distress related to clinical assessments and neurofeedback.** Some of the questions may be distressing to Participants and young adults with internalizing symptoms because of inducing low levels of negative self-focused cognitions. Additionally, anxious individuals can easily feel overwhelmed or fatigued by what would be minimally demanding tasks for others, such as filling out these assessments. Voluntary neuromodulation is not easy, some participants may feel frustrated or sad due to perceived inability to complete the task.

5. **Risks related to MRI**

- a. ***Claustrophobia.*** Some people experience fear while inside the scanner due to its confining space.
- b. ***Magnetic pull-on metal objects.*** The strong magnetic field in the scanner could cause any foreign metal bodies implants in the participants to change position, injuring them.
- c. ***Scanner noise.*** The noise generated from the operation of the scanner is loud and can damage hearing without protection.
- d. ***Mild symptoms.*** Some people experience mild, short-term symptoms while in the scanner, including headaches, dizziness, mild nausea, metallic taste, and/or the sensation of flashing lights. These symptoms resolve shortly after removal from the magnetic field.
- e. ***Boredom.*** MRI scans involve a large time commitment, and participants may become bored.
- f. ***Potential for discovery of brain abnormalities.*** It is possible that the MRI scan would reveal unknown and unlooked for abnormalities. We will refer the family to a radiologist (covered by the family's insurance) and provide them with a copy of the structural images if so desired.

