Communication with research participants will also take place outside of treatment settings. If this box is selected, please describe the type of communication and how it will be received by participants.

We will communicate with participants verbally over the phone, via texts and emails (primarily for scheduling purposes), and in person. However, participants and their families may receive copies of the consent and assent forms in advance of their first session via email if they want to see the forms in advance. Email and texts will be also used primarily to confirm appointment times and dates and for participants to cancel if they wish to. Any time before or after consent and assent are signed, participants will have the option to sign a written authorization for text and email (in a form approved by **HIPCO**). For example, to permit the use of unencrypted emails for more detailed communication of information if they wish it about their research participation such as communication about eligibility and health information. This will also allow participants to receive an email with a summary of key findings after signing consent and assent form

19.6 Explain how the research team has legitimate access to patients/potential participants:

The research team will be permitted to access healthcare records with a completed **HIPAA** form. The data derived from the healthcare records are for the purpose of obtaining details about frequency and or history of prior hospitalization, prior diagnoses, presence of prior suicide attempts, and current or past medication. Data derived from the healthcare records could include reported instances of abuse that might not have been disclosed to the research staff and/or clinical history characteristics that investigators might have run out of time to collect or inquire about during the first visit.

19.7 Location(s) of storage, sharing and analysis of research data, including any links to research data (check all that apply).

In the data shelter of the [Information Exchange \(IE\)](#)

Store Analyze Share

In the Bone Marrow Transplant (BMT) database, also known as the HSCT (Hematopoietic Stem Cell Transplant) Database

Store Analyze Share

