Data access will be limited to the Investigators and study staff who will receive human participants training and certification through the CITI curriculum. Any staff member who has access to participants or data will receive training in the critical importance of participant confidentiality. Every effort, and ongoing adjustments, will be made to ensure that the identity of participants will not be able to be determined using the data. Future use of the data includes research, demonstration, publication, public performance, and archiving. Participants' permission for further use of their data, in de-identified form, will be obtained in the initial consent form. As stated, ID will link data to participant's personal health information in an excel, passworded document kept in the academic health center (AHC) secure server or Box secure storage. The excel document containing the links between the numbers and the participant's information will be destroyed after all publications of the study pertaining to the identified principal outcomes are concluded.

Participants will be assured that sensitive information about their relationship with their parents, their sexual orientation, sexual experiences, experimental drug use or other sensitive information will not be shared with their parents. However, both participants and parents will be advised that there will be exceptions in confidentiality that include new knowledge of abuse of vulnerable children or adults, impending and concrete risks of harm to self or others. Part of the interview entails describing instances, methods and emotions surrounding prior suicide attempts. Every effort will be made to convey the expertise and comfort of the research staff with this information and to acknowledge and validate any feelings of discomfort that such disclosure might elicit in the participant. Similarly, the interview entails disclosing past instances of exposure to abuse or maltreatment, and the staff will support participant's emotions or feelings during the interview, offer breaks, verbal comfort, and validation of their emotions. Participants will be encouraged to disclose information in their own time and to the extent that they feel comfortable with.

23. Access to Participants.

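### Section 7.1 emails caregivers a summary of the child's questionnaires on request, which conflicts with the confidentiality promised elsewhere and is not held until the last outcome visit

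*Combined protocol and SAP*

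**What the plan says.** Section 7.1 makes the caregiver's written request the trigger for release: "Results will not be shared with participants unless guardians/parents/caregivers specifically request them in writing (via email to the PI". On such a request, "a summary of key questionnaires, (i.e., one paragraph) will be emailed to the caregiver". Unscored protocols are withheld. The same section then advises: "Psychological findings and results are not recommended to be disseminated in the absence of a feedback session with a licensed mental health practitioner".

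Other sections describe what parents will learn:

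- Section 16.1, item 3 (loss of confidentiality): participants' information "will be kept confidential from their parents, except in the case where danger to self or others is identified".
- Section 16, paragraph on disclosure of health risk behaviours: information is confidential unless someone is in danger, with suicidality among the examples. Staff are to speak with the adolescent before parents are told.
- Section 22: participants are assured that matters such as their relationship with their parents, "sexual experiences, experimental drug use or other sensitive information will not be shared with their parents", with exceptions for abuse and for concrete risk of harm.
- Section 19.5: a written authorization for unencrypted email will also let participants "receive an email with a summary of key findings after signing consent and assent form".

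Section 3.1 lists self-reported suicide ideation in the R61 primary outcome and adds the C-SSRS and SIQ for R33. Table 1 schedules the SIQ, DERS, SPPA and RD at all five visits.

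**The concern.** Two things are at stake.

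The first is the promise made to the adolescent. The battery in Section 5.1 includes the Child Trauma Questionnaire, the adolescent Conflict Behavior Questionnaire and self-harm inventories. Some of these ask about the household. Nothing in Section 7.1 keeps them out of a summary sent to a caregiver, and the sections that promise confidentiality do not mention that such a summary exists.

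The second is the quality of later self-report. An adolescent who learns that a parent has read a summary of Visit 1 answers has a reason to disclose less at Visits 2 to 5. In the R61 phase both groups train an active locus (dACC or right amygdala). Reduced reporting after a release would there look the same as improvement after neurofeedback.

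**Working it through.** The plan gives no figure to reproduce on this point. The check is a comparison of texts, followed by an illustration based on assumed inputs.

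**1. The release rule against the promises**

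| Question | Section 7.1 | Sections 16 and 22 |
|---|---|---|
| Who decides? | Caregiver, by email | Staff, when danger (Section 22 adds abuse) is identified |
| What is released? | Key questionnaires, not listed | Only what falls under the stated exceptions |
| Is the adolescent involved? | No step stated | Staff talk with the adolescent before parents are told (health risk behaviours) |
| Is the other route mentioned? | No | No |

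The two columns agree only if the summary is confined to content outside the promise. Section 7.1 does not confine it.

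**2. Timing.** Section 7.1 gives no release date. The only related wording is in Section 19.5, which places an emailed summary after the forms are signed. No text delays release until the outcome visits are over, so a request after Visit 1 would come before four further rounds of self-report.

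**3. Which analyses are exposed**

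- *R61 milestones.* Milestone 1 uses regional activity and connectivity. Milestone 2 uses the ETB and IAT. Neither uses questionnaire ideation.
- *R61 secondary use.* Section 18 correlates connectivity change with change in DERS, SPPA and RD. Under-reporting unrelated to connectivity change adds noise to these correlations. A simple pre-post reading of self-report, with no control arm, would be shifted.
- *R33.* With 70 participants randomized 1:1 (35 per arm), equal under-reporting cancels from the between-arm mean difference.

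**4. Illustration of size.** Let f be the share of families in which a release changes reporting, and k the under-reporting in SDs of change. The documents give neither, so I assume f of 10% to 50% and k of 0.25 to 1.0.

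Shift in mean change = f × k. Lowest: 0.10 × 0.25 = 0.025 SD. Middle: 0.25 × 0.5 = 0.125 SD. Highest: 0.50 × 1.0 = 0.50 SD.

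The table gives the chance that a two-sided 5% paired t-test is significant with no true change (noncentral t, n − 1 degrees of freedom, noncentrality f × k × √n, SD of change held at 1). The sizes are 20 per locus and 40 in total, from Section 18.

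| Shift (SD) | n = 20 | n = 40 |
|---|---|---|
| 0.025 | 5.1% | 5.3% |
| 0.05 | 5.5% | 6.1% |
| 0.10 | 7.1% | 9.5% |
| 0.125 | 8.3% | 12.0% |
| 0.25 | 18.6% | 33.8% |
| 0.50 | 56.5% | 86.9% |

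Section 18 specifies no R61 pre-post test of ideation, so this describes an informal before-after reading and not a planned test.

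For R33 the bias is (f × k in the active arm) − (f × k in the control arm), which is 0 when the two are equal. The added variance of change is f(1 − f)k². With f = 0.25 and k = 0.5 this is 0.25 × 0.75 × 0.25 = 0.047, so the SD rises to √1.047 = 1.023, about 2%. If under-reporting occurred only in the active arm, the false-positive rate with 35 per arm would run from 5.1% to 54.1% over the same range. I found no statement on blinding of participants or caregivers that would rule out a difference between arms, but the documents give no reason to expect one.

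**The case against.** The strongest reply is that suicide ideation is the information least protected from parents in this protocol. Danger to self is an exception in Section 16.1, and suicidality is named as one in the paragraph on health risk behaviours. Section 16.2 involves parents to inform them of the current risk. Section 16.4 has safety plans made with the attending caregiver, counts caregiver awareness of C-SSRS scores of 4 or 5 as a protective factor, and relies on caregivers' statements about safety at home. Much of any incentive to under-report severe ideation therefore exists without Section 7.1 and would remain after the fix. This stands. What Section 7.1 adds falls mainly on lower-level ideation and on family or other sensitive items.

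It is also fair to say that raw protocols are withheld, and that a scored paragraph written with Section 22 in mind could satisfy both sections. That is possible, but nothing in Section 7.1 requires it. The consent and assent forms are not in the text available to me, so I cannot say whether they describe this route.

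A reader might also draw stronger conclusions that the documents do not support:

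- *That parents will be sent SIQ results.* The key questionnaires are undefined, so this is possible but not shown.
- *That release at any time is expressly allowed.* This is an inference from silence and the Section 19.5 wording.
- *That adults can never obtain their own results.* Section 7.1 alone reads that way, but Section 19.5 has participants receiving a summary.
- *That Section 7.1 flatly contradicts itself.* The feedback-session sentence is a recommendation, so emailing the summary is in tension with it but does not break a rule.

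**Conclusion.** The conflict of wording is real and rests on no assumption. A caregiver's request alone releases a summary of the adolescent's questionnaires, while Sections 16.1 and 22 promise confidentiality from parents and the health-risk paragraph has staff speak to the adolescent first. No text holds the release until the repeated self-report is complete.

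The effect on outcomes is plausible but of unknown size. The range of 0.025 to 0.50 SD depends entirely on assumed values of f and k, and it overstates what Section 7.1 adds wherever caregivers already know of the ideation. Setting it against the d of 0.4 in Milestone 1 would mislead, because that threshold applies to neural measures. The documents do not support a claim that the go/no-go decision is at risk, or that the R33 contrast is biased without a difference between arms. The exposure is to uncontrolled before-after readings of self-report in R61, with a little added noise elsewhere. The change is worth making because it protects confidentiality and candid reporting at very low cost.

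**What to change.** Revise Section 7.1 as follows:

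1. Release no questionnaire summary until the participant's Visit 5 is complete. For adults with borderline personality disorder who complete only four sessions, use their last visit. Leave the existing Section 16 safety disclosures unchanged.
2. Limit the summary to content that the assent form lists as shareable with parents, and exclude the material protected by Section 22.
3. For participants aged 18 or over, including those who turn 18 during the study, send the summary to the participant on the participant's own request, consistent with Section 19.5.
4. Reconcile Section 7.1 with Section 16.1, the Section 16 paragraph on health risk behaviours, Section 19.5 and Section 22, and use the same wording in the assent form.
5. Reconcile the advice on feedback sessions with the email route. This can be done in wording and need not create a new session.

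It would also help to log the date of any release that has already happened, so that those participants can be left out in a sensitivity analysis of self-report.

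The cost is a text amendment and a matching line in the consent and assent forms. Families wait until Visit 5 for a one-paragraph summary. No new data collection or practitioner time is needed.

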7.2 Sharing of genetic testing: **N/A.**

8. Study Population

8.1 Inclusion Criteria:

a) 1st-time suicide attempting participants (**11-18 years**) with current suicide ideation. However, if within the first 3 months of the project starting participant recruitment it is difficult to recruit the targeted number of participants, **the study population will be expanded to any suicide attempting participants without restricting to 1st time attempters, and we could also include first time attempters with low or no suicide ideation.** This flexibility to recruitment criteria is implicit in our protocol if recruiting 1st time attempters with lingering ideation proves to be very difficult.

We will also include participants with any level of depression and: 1. current suicide ideation, 2. no current suicide ideation but a history of past suicide ideation, 3. neither past nor present suicide ideation.

History of suicide attempts, suicide ideation, and depression levels will be ascertained during the phone screening. During the first session, suicide ideation levels will be ascertained using the suicide ideation questionnaire or a similar approved short questionnaire. Any criteria not specifically coded for by the BPIC will be tested by study and the research staff, e.g., IQ and handedness. If targeted clinical population participants become 18 during the project, they will be re-consented with the adult consent form.

b) Adult individuals (18 -45 years old) with Borderline Personality Disorder (BPD) symptoms or youth with BPD traits (17yrs.) regardless of their history of suicide ideation or attempts.

8.2 Exclusion Criteria: Please see Table 2.

Table 2. Inclusion and Exclusion Criteria	
Inclusion R61-R33	Exclusion R61-R33

a) 11-18 years old, right or left-handed, gender balanced participants. Depressive Disorders, PTSD.
 
1. Suicide ideation ~1 standard deviation in the suicide ideation questionnaire ²⁹ and/or a suicide attempt (within the last year or at any time in their life).
 
2. Depressed participants regardless of their history of suicide attempts with any current or past levels of suicide ideation. Comorbid anxiety disorders, eating disorder symptoms & experimental substance use allowed. Stable medication and therapy allowed (~ 2 weeks of treatment), however the latter can be relaxed to increase accrual.
	
MRI contraindicated (e.g., claustrophobia or pacemakers or other metal implants incompatible with MRI). History of traumatic brain injury. IQ<75. Severe or acute medical illnesses that require multiple hospitalizations. History of severe brain damage, frequent/current seizures, mental retardation, or serious neurological disorder that affects brain structure. Previous history or current diagnosis of Schizophrenia, or Autism. Refusal to cooperate with study procedures. High acute, imminent suicide attempts risk. Please see the Suicide Risk Assessment section for criteria to determine this risk. [name], and [name], PhD. will consult each other and triage the need for hospitalization, emergency room escort, and medication adjustment for participants with acute suicide risks. An additional level of safety may include “on-call” mental health workers that staff can consult to determine exclusion.
 
A current diagnosis of a substance use disorder. Primary psychotic disorder or active psychosis. Active substance abuse disorder or primary diagnosis of anorexia disorders. Symptoms of anorexia disorders are not considered exclusionary criteria.


b) Adult individuals (18-45 years old) with Borderline Personality Disorder (BPD) symptoms or youth with BPD traits (17 yrs.)
	
MRI contraindicated (e.g., claustrophobia or pacemakers or other metal implants incompatible with MRI). History of traumatic brain injury. IQ<75. Severe or acute medical illnesses that require multiple hospitalizations. History of severe brain damage, frequent/current seizures, mental retardation, or serious neurological disorder that affects brain structure. Previous history or current diagnosis of Schizophrenia, or Autism. Primary psychotic disorder Refusal to cooperate with study procedures. High acute, imminent suicide attempts risk. Please see the Suicide Risk Assessment section for

	criteria to determine this risk. Psychiatrist, MD, and [name], PhD. will consult each other and triage the need for hospitalization, emergency room escort, and medication adjustment for participants with acute suicide risks. An additional level of safety may include “on-call” mental health workers that staff can consult to determine exclusion.
--	--

Healthy control 11-18 year old Participants (N~ 15) volunteers. balanced in gender who do not meet any of the criteria for diagnostic risks (i.e. no current psychological illness or past history of suicide attempts) will be included in the initial stage of the research to train personnel and test the procedures in healthy participants, while PI and research staff leads all procedures, prepare data sets and pipelines and while recruitment procedures and community contacts are developed by the researchers. Healthy adolescent volunteers may not be compensated but recruited from the community to voluntarily participate to advance neuropsychological research. If monetary compensation is required (e.g., due to the burden of the tests and days/hours the participants and their family is involved or preferred by the healthy volunteer and their family, it will be at the indicated lower rates in the compensation section. Healthy volunteer data will be used for data analyses or publication if of enough completion, quality and/or sample size.

Similarly, **healthy adult volunteers** – accrued via the CMRR adult volunteer program or recruited among study adult volunteer graduate or undergraduate students or in the general population (but using the present IRB protocol) will be included in the initial stages of the research to train personnel, analyze data and pilot the data collection procedures. Healthy adult volunteers will include the PI ([name]) who will pilot the fMRI tasks and all the tasks by herself without compensation. Healthy adult volunteers could be undergraduate research assistants that will volunteer without monetary compensation due to their interest in the research itself or in exchange for research credit/hours at the University of Minnesota or in any local University.

9. Screening

We will accrue a data set of participants (**ages 11-18**) across levels of suicide ideation, defined as **SIQ**²⁹ total score or other similar approved questionnaire that can be quickly administered over the phone or during the first session. History of suicide attempts will be identified at recruitment and confirmed later with an in-person interview using the C-SSRS,⁴⁹ and the K-SADS,²⁶ and other suicide ideation questionnaires. Caregivers will complete questionnaires about children and about themselves, they are included in the research even if they have medical psychiatric conditions. Parents **are not** the focus of the research, but they will provide information about their own mental health history, their children’s mental health history, some of the parent’s current symptoms if applicable and their relationship and the rearing environment. We will also recruit adult individuals with symptoms of Borderline Personality Disorder (BPD) or youth BPD traits (17 yrs.)

10. Vulnerable Populations

Population / Group	Identify whether any of the following populations will be targeted, included (not necessarily targeted) or excluded from participation in the study.
1. Children	Targeted Population
2. Pregnant women/fetuses/neonates	Excluded from Participation
3. Prisoners	Excluded from Participation
4. Adults lacking capacity to consent and/or adults with diminished capacity to consent, including, but not limited to, those with acute medical conditions, psychiatric disorders, neurologic disorders, developmental disorders, and behavioral disorders	Excluded from Participation
5. Non-English speakers	Included/Allowed to Participate
6. Those unable to read (illiterate)	Excluded from Participation
7. Employees of the researcher	Included/Allowed to Participate

8. Students of the researcher	Included/Allowed to Participate
9. Undervalued or disenfranchised social group	Included/Allowed to Participate
10. Active members of the military (service members), DoD personnel (including civilian employees)	Included/Allowed to Participate
11. Individual or group that is approached for participation in research during a stressful situation such as emergency room setting, childbirth (labor), etc.	Targeted Population
12. Individual or group that is disadvantaged in the distribution of social goods and services such as income, housing, transportation, or healthcare.	Included/Allowed to Participate
13. Individual or group with a serious health condition for which there are no satisfactory standard treatments.	Included/Allowed to Participate
15. Individual or group with a fear of negative consequences for not participating in the research (e.g., institutionalization, deportation, disclosure of stigmatizing behavior).	Included/Allowed to Participate
16. Any other circumstance/dynamic that could increase vulnerability to coercion or exploitation that might influence consent to research or decision to continue in research.	Included/Allowed to Participate

10.1 Additional Safeguards: A data safety and monitoring board (DSMB) and an independent medical monitor, specifically Presently, **an independent medical monitor IMM** will monitor the research procedures and the safety of the participants. Please see the attached data safety and monitoring plan (DSMP) uploaded in ETHOS.

Please note that regarding Table 9 Vulnerable Populations: The following assurances apply to all of them, they will be informed of the risks and benefits of the research, their information will be kept confidential, and they will have freedom to decline and withdraw from the research at any point. Their inclusion and participation will be subject to the monitoring by a DSMB and an IMM. The inclusion of adults lacking capacity to consent and/or adults with diminished capacity to consent, members of the military or disadvantaged individuals is made to provide for assurances regarding the participant's parents. While parents are not the focus of the research, they will be asked to complete questionnaires about themselves and about their offspring.

Regarding Population (1) Children. Consent from parents/caregiver will be obtained via a signed consent form and clear concise verbal explanation of the research goals, procedures. Participant's confidentiality will be assured but parents and their children will be informed of limitations of confidentiality regarding danger to self, others, and impending risks of suicide attempts. Meaningful assent via a signed form will be also obtained from the Participants. Only one parent or caregiver will be needed to provide consent. If the adolescent turns 18 while still in the study, they will sign a consent form in the next scheduled visit before any further research procedures take place. Participants and their families will be informed of their freedom to decline and withdraw from the research at any point without penalty. Participants and the parent/caregiver will sign a **HIPPA form to grant access to medical records, this might also be an additional form that is standard to each clinic and will be uploaded to ETHOS in addition to the HIPPA portion in the consent/assent forms.**

Regarding Population (5.) Non-English Speakers only Spanish speaking participants and parents will be included as the PI's [name] first language is Spanish. **Please see the consent section for procedures to be followed with this population.** The same assurances regarding confidentiality, freedom to withdraw and monitoring apply to all participants. Participants need to be able to speak and read English fluently and/or be bilingual Spanish/English speakers to be included, parents who speak limited English but who primarily speak Spanish can be included.

Regarding Population (8.) Students or Employees students and research assistants and employees will be allowed to participate as pilot adult participants if they wish it. This will not be a condition for their accrual of research credits, for their continued

employment, or for their participation as research assistants or employees in research conducted by [name] at the University of Minnesota. The same assurances regarding confidentiality, freedom to withdraw and monitoring apply to all participants. The CMRR has a pool of adult volunteers to test emerging protocols and healthy adult volunteers may be reached to pilot the research.

Regarding Population (11.) Individual or group in stressful situations. Participants and/or their parents will be approached for respectively contact information of their parents and information to call and offer the opportunity for participation. Clinical or research personnel will extend permissions to contact to participants and/or their parents. The permission to contact documents will also be included in the folder that families review during admittance to emergency room or inpatient units. Both participants and their parents may be approached while participants are in inpatient units or in emergency rooms by clinical personnel or by research staff (after been assured by the clinical personnel of their suitability for research). However, all care will be taken so that Participants and their parents understand that quality or provision of care is independent and unaffected by their decision to participate. The same assurances regarding confidentiality, freedom to withdraw and monitoring apply to all participants. Additional safeguards in this study may include assessment of suitability for inclusion in the present research by an independent medical monitor (**an accredited mental health provider**). Establishing independent capacity to consent assessment will be done using the UBACC for adolescent participants over 18. For participants under 18, the teach-back method may be used during the consent process to establish the parent's and child's understanding of the study. Please see the **DSMP uploaded in ETHOS**. We will also ensure confidentiality as well as ensure that potential research participants are free to decline joining the study or drop out at any point.

Regarding Population (12.) Individual or group that are disadvantaged. Participants and/or their parents will be provided with a form to provide consent for the staff arranging transportation for research participants during the screening process and at any point throughout the study during which participants or parents are not able to provide transportation. The study team can arrange transportation for research participants via a 3rd party vendor (including but not limited to Taxi services, Uber, Lyft, or an airplane ticket).

- **This study's significance** rests on the relevance of our clinical target for life-span suicide risks. If successful, this project: (i) will yield an intervention to be used alone or in combination with current pharmacological or psychological interventions; (ii) could be expanded and tested with other financially viable biofeedback modalities; (iii) will increase knowledge of neurobehavioral mechanisms of NF's effectiveness to elicit corrective neuroplasticity in circuitry of affect regulation and self-processing; (iv) will inspire new therapies to modify self-processing and affect regulation across diagnostic categories.
- Participants with a recent suicide attempt and occasional suicide ideation are the least impaired participants among which a novel neurofeedback non-invasive treatment of suicide ideation can be tested. Participants who are still acutely suicidal (who report concrete, impending and clear plans for suicide attempts and who cannot commit to not attempting suicide) are excluded from the study as their needs for hospitalization and immediate treatment supersede the aims of this study. They can return to the study after the acuity and risk diminishes. Similar risks apply to adult individuals with a Borderline Personality Disorder (BPD) or BPD traits patients (18-45 yrs.).
- A later section discusses the risks that this research entails. Briefly, participant's confidentiality will be preserved, participants and their caregivers will be free to decline to participate and will have the right to withdraw at any time without penalty. Parental consent and adolescent assent will be obtained via a signed assent and consent forms.

11. Local Number of Participants

11.1 Local Number of Participants to be Consented:

R61 phase. During the 2-year R61 phase, we anticipate screening **~470 participants including ~70 adults** using standard MRI eligibility questions and screening for suicide ideation and attempts. A **maximum of 150 participants** will agree to participate and will undergo baseline tests and pre- NF training tasks. Some attrition is expected due to movement and treatment discontinuation. **60 participants are the minimum** that will allow data analysis and complete all post-NF assessments and 1-month follow-up assessment, yielding 20 data sets per NF target with high quality scans and pre and post NF training data in the R61 phase.

R33 phase. We anticipate screening **~700** contacts for MRI eligibility over 3 years in the R33 phase. We expect that approximately **300 Participants may** perform baseline evaluations and pre-treatment tasks and to garner **~90** high quality scans for all NF sessions randomly assigned to active (**dACC or Right-Amygdala** depending on research phase) versus Unrelated-NF. **70** (minimal number for analysis) and complete pre and post NF-training phenotypical data and high-quality NF scans.

12. Local Recruitment Methods

12.1 Recruitment Process:

We will seek referrals from the Adolescent Inpatient Units at the University of Minnesota (U of M) MHealth Fairview, from the Washburn Children's and Fairview Clinics, the Minneapolis School Clinics, Children's Hospitals and the Emily Program as well as other mental health institutions in the Twin Cities area including Emergency Rooms. Clinicians within inpatient units will extend brief permission to contact forms to participants or their parents. Clinicians can also point out parents or participants to a Quick Response (QR) code that will trigger a permission to contact the used phone number to initiate the screening process. This method is particularly important to protect clinicians, participants and their family and the research staff from in person close contact in closed units to avoid contagion related to epidemics or other contagion agents.

Clinicians can inform research staff about specific patients that are suitable for research and research staff will then extend the permission to contact to the adolescent or their parents/caregivers. Clinicians will not explain the research in detail beyond what will be posted in the permission to contact forms or flyers. Instead, the contact forms or the **Quick Response (QR) code** will give researchers permission to call parents or Participants and explain the research over the phone and schedule an in-person or remote video call consent process. Additionally, individuals that might extend permission to contacts or use the Quick Response (QR) code include ER staff, doctors, therapists, social workers, pediatricians, or teachers. Both research staff and other referring personnel that extend permissions to contact or Quick Response (QR) code prompts will limit the effects of coercion by ensuring that patients and their caregivers understand that:

1st their decision to participate or not does not affect the quality or availability of care.

